## 3.2 AIM TWO

Identify the potential barriers and facilitators to the widespread implementation of VR for perioperative anxiety

### THEORETICAL FRAMEWORK

The interview schedule and analysis will be informed by the Consolidated Framework for Implementation Research (CFIR), which is a highly organised explanatory framework that identifies factors that potentially influence implementation success (Damschroder et al., 2009). The CFIR is well suited to facilitate the rapid-cycle evaluation of the implementation of complex health care delivery interventions, as it provides a comprehensive framework for systematically identifying variables that may occur in various, multi-level contexts to affect implementation (Keith, Crosson, O'Malley, Cromp, & Taylor, 2017). The CFIR is organised across five domains; each of these could affect the implementation of an intervention. Firstly, the characteristics of the intervention, which are the features of an intervention that might influence implementation. There are eight constructs included in this domain. Secondly, the inner setting, which includes the implementing organization features that might influence implementation. There are 12 constructs included in this domain. Thirdly, the outer setting, which includes the external context or environment features that might influence implementation. There are four constructs included in this domain. Fourthly, characteristics of the Individuals involved in implementation that might influence implementation. There are five constructs included in this domain. Finally, the implementation process, which includes strategies that might influence implementation. Eight constructs are included in this domain (Damschroder & Lowery, 2013). See CFIR website http://cfirwiki.net/guide/app/index.html#/

# PARTICIPANTS AND RECRUITMENT

Semi-structured interviews will be conducted with 20 stakeholders or until data saturation is reached. Saturation is reached by sampling to the point when redundancy or repetition of the data in a particular sample yields no new information (Crabtree, Miller, Crabtree, & Miller, 1999; Francis, Tatam, & Groves, 2010). Purposive maximum variation sampling will be used to capture a wide range of stakeholders' perspectives relating to the intervention. The semi-structured interviews will be conducted with a variety of stakeholders, including department heads, medical staff, nurses, administrative staff, and patients. Patients who signed the consent form agreeing to be interviewed will be followed up by the PhD candidate. Consecutive patients will be interviewed on a first come first-served basis before they are discharged. Other stakeholders will be contacted via email by the clinical research coordinator of the hospital on behaving the PhD candidate. The main principle underpinning participant selection for an interview will be that they experienced VR either as a clinician, administrator, or patient.

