## **RESEARCH AIMS**

The aims of this study are:

- 1- To evaluate the effectiveness of using VR technology for perioperative anxiety among adults undergoing elective surgery.
- 2- To identify the potential barriers and facilitators to the widespread implementation of VR for perioperative anxiety

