### **RISK AND BENEFITS**

There are possible risks associated with participating in this study include discomfort, headache, stomach awareness, nausea, vomiting, pallor, sweating, fatigue, drowsiness, disorientation, and apathy (Hicks & Durbin, 2011).; however, if the intervention is effective, people in the intervention group may experience reduced perioperative anxiety.

The participants will be monitored by the researcher continuously to assess for side effects. If a side effect occurs, the Virtual Reality session will be ceased immediately and treating doctor will be consulted.

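### Selecting interviewees on having experienced VR leaves out VR-arm patients who never start a session and reaches early stoppers only by chance, so patient-level barriers are likely to be under-represented in Aim 2

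*Protocol*

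**What the plan says.** The second aim, under Research Aims, is "To identify the potential barriers and facilitators to the widespread implementation of VR for perioperative anxiety". The Participants and Recruitment section of Aim Two sets out who is interviewed:

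- Number: "Semi-structured interviews will be conducted with 20 stakeholders or until data saturation is reached".
- Groups: five, "including department heads, medical staff, nurses, administrative staff, and patients".
- Approach: "Purposive maximum variation sampling will be used to capture a wide range of stakeholders' perspectives relating to the intervention".
- Order for patients, among those who agreed to interview: "Consecutive patients will be interviewed on a first come first-served basis before they are discharged".
- Selection: "The main principle underpinning participant selection for an interview will be that they experienced VR either as a clinician, administrator, or patient".

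Risk and Benefits foresees that some sessions will not be completed: "If a side effect occurs, the Virtual Reality session will be ceased immediately and treating doctor will be consulted". No section provides for interviewing a VR-arm patient who never started a session, or for deliberately seeking out those who stopped.

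**The concern.** For an aim about uptake, choosing patients because they took the intervention up is selection on something close to the outcome. Declining the headset, missing the session and stopping for discomfort are among the most direct signs of a patient-level barrier. The first two groups fall outside the selection principle. The third falls inside it, but nothing ensures that any of them is heard.

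At stake are the ratings described in Data Collection and Analysis, where each CFIR construct is rated for the direction and strength of its influence. If the patient input comes mainly from people for whom delivery worked, acceptability barriers may be rated too low or not surface. The Study Design section presents the hybrid design as a route to rapid implementation, so such a gap would carry into advice on roll-out. The randomised comparison and the primary outcome are not affected.

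**Working it through.** The protocol gives no figure for this point beyond the planned 20 interviews, so there is no calculation of its own to reproduce. The check is a comparison of the text with four patient situations, followed by an illustration.

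**Who meets the selection principle**

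| VR-arm patient | Experienced VR? | Position under the protocol |
|---|---|---|
| Completed the session | Yes | Eligible, taken in order |
| Session stopped early | Yes, in part | Eligible, taken in order, not sought |
| Declined the headset | No | Does not meet the principle |
| Session never took place | No | Does not meet the principle |

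**Does another provision repair this?**

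- Maximum variation sampling would do so if applied to patients, but the section then takes patients consecutively, which does not select for variation in how delivery went.
- The saturation rule does not. The section defines saturation as redundancy within a particular sample, and a sample of people exposed to VR can become redundant without including anyone who declined.
- The sample interview questions are addressed to department heads, medical staff, nurses and administrative staff; none is addressed to patients.

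**How often consecutive recruitment would miss early stoppers**

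Inputs:

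- m, the number of patient interviews. Not stated. Assumed 4 (20 interviews ÷ 5 groups, an even split) or 8.
- p, the proportion of started sessions stopped early. Not stated. Assumed 2%, 5%, 10% or 20%.
- Interviewed patients are treated as independent draws from those who started VR.

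Formula: P(no early stopper among m) = (1 − p)^m.

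| p | m = 4 | m = 8 |
|---|---|---|
| 2% | 0.98^4 = 0.92 | 0.98^8 = 0.85 |
| 5% | 0.95^4 = 0.81 | 0.95^8 = 0.66 |
| 10% | 0.90^4 = 0.66 | 0.90^8 = 0.43 |
| 20% | 0.80^4 = 0.41 | 0.80^8 = 0.17 |

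With 75 patients per group (Sample Size), the expected number of early stoppers if all started would be 75p: 1.5, 3.75, 7.5 and 15. Except perhaps at the lowest rate, there would usually be some to approach, subject to their agreeing to interview.

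The table concerns early stoppers only. For patients who never started, the gap comes from the selection principle and does not depend on a rate. How many there would be cannot be estimated from the protocol.

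**The case against.** The case on the other side has real weight.

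- **The wording is a main principle, not an exclusion criterion.** A reader might infer that interviews are strictly limited to people who used VR, so that a decliner could never be interviewed. The text does not go that far, and the same paragraph commits to a wide range of perspectives. What stands is that decliners fail the one selection principle given and nothing else provides for them.
- **Early stoppers qualify.** So do patients who finished with nausea or eyestrain. A reader might infer that Aim 2 misses the people who met the barriers; the protocol does not support that. Early stoppers are not targeted, which is a lesser fault.
- **Four of the five groups are staff.** The sample questions cover complexity, self-efficacy, implementation climate and patient needs, and staff may explain better than a patient why a session did not happen. This stands for organisational and workflow barriers. It is weaker for individual acceptability: under Blinding, clinicians are not told who takes part or in which arm, and under Risk and Benefits it is the researcher who monitors participants for side effects.
- **Intolerance is recorded elsewhere.** The Virtual Reality Symptom Questionnaire covers 13 symptoms in the intervention group. It records symptoms, not reasons for declining.
- **Refusal may be rare.** Patients consent beforehand, a history of motion sickness is an exclusion, and exposure is short and seated. That is plausible, and it is why the illustration spans a range.

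That the conclusion would tilt in favour of VR is also tempting to infer. It is a reasonable worry, but the protocol gives nothing from which a tilt could be shown or sized.

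**Conclusion.** The point holds as a minor weakness in the sampling for Aim 2. VR-arm patients who decline the headset or whose session never takes place do not meet the stated selection principle. Those who stop early are eligible but reached only by chance, because consecutive recruitment does not carry out the maximum variation sampling that the same section names. Patient-level acceptability barriers are likely to be under-represented.

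The size is uncertain. Over the assumed ranges, the chance of hearing no early stopper runs from about 17% (8 interviews, 20% stopping) to about 92% (4 interviews, 2% stopping). No single value in that range should be quoted as the size of the fault: both inputs are assumptions, and the figures measure the effect of taking patients in order, not the effect of the selection principle on those who never started.

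**What to change.** In Participants and Recruitment, change the patient part of the selection principle to: *were allocated to VR, whether or not the session was started or completed*. The parts for clinicians and administrators can stay.

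Replace consecutive recruitment of patients with the maximum variation sampling already named: approach purposively those who declined, missed or stopped the session, as well as completers. Restrict this to patients who agreed to interview and have not withdrawn, since Participant Rights allows withdrawal without explanation. No fixed quota is needed.

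The cost is a wording change within the same planned number of interviews, the need to note which VR-arm patients did not start or finish, and slightly fewer interviews with completers.

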### DATA COLLECTION AND ANALYSIS

All interviews will be conducted face-to-face by the PhD candidate at any time point from the beginning of the study to the end (estimated study period is four months). The potential participants will choose the location and time of the interview. The interviews will be audio-recorded and transcribed verbatim. The interviews will be structured around the five CFIR domains and included questions guides drawn from online CFIR http://cfirwiki.net/guide/app/guide.html as a start point for the PhD candidate to commence the interviews.

The following is a sample of semi-structured interview questions by stakeholder group:

Stakeholder Group	Question	CFIR Domain(s)	Constructs
Department Heads	How well do you think the VR will meet the needs of the individuals served by your department?	Outer setting	Patient Needs & Resources
Medical Staff	How complicated is the virtual reality?	Characteristics of the intervention	Complexity
Nurses	How confident are you that you will be able to successfully implement the VR?	Characteristics of individuals	Self-efficacy
Administrative	What is the general level of receptivity	Innersetting	Implementation
Staff	in your organization to implementing the VR?		Climate
Department Heads	What are influential individuals saying about the VR?	Process	Opinion leaders
	-Who are these influential individuals?		
	-To what extent will they influence		
	others' use of the VR the success of the implementation?		

The transcribed interviews will be analyzed using qualitative content analysis techniques, inspired by a deductive directed approach. This approach is recommended for CFIR (Keith et al., 2017). Data

Study Protocol

analysis will begin simultaneously with data collection to guide the PhD candidate to modify the interview's questions. The analysis will be performed by two researchers independently by using the CFIR NVivo template - pre-populated with construct codes. Firstly, reading all transcripts to obtain a general overview to develop initial coding nodes and subnodes based on the domains and constructs of the CFIR framework (Damschroder et al., 2009). Secondly, units of analysis, such as sentences or longer semantic units, will be deductively coded into the nodes and subnodes. Thirdly, the coded text will then be subjected to a rating process following the recommended method by CFIR author (Damschroder et al., 2009). In the rating process, a deliberated consensus process will be used to assign a rating to each construct obtained from each interviewer. The ratings reflect the positive or negative influence and the magnitude or strength of each construct. To organize and manage a large amount of data, the software program NVivo version 12 will be used.

# QUALITATIVE RIGOR

To enhance trustworthiness, credibility, transferability, dependability, and confirmability will be assessed. Credibility will be ensured by peer debriefing and support, which will occur by regular meetings with the research team to share study processes and findings to identify biases also to support each other. Transferability will be ensured by using a thick description, which provides a comprehensive explanation of the study context, including the cultural and social contexts during data collection. Dependability and conformability will be ensured by maintaining the audit trail, which includes audio recordings, transcripts of interviews, and documents for data analysis (Cypress, 2017; Moser & Korstjens, 2018).

# 3.3 ETHICAL CONSIDERATIONS

# ETHICAL CONDUCT

Before the commencement of this study, approval of the study will be obtained from:

- 1. Ethical Committee at the University of Newcastle
- 2. Independent Ethical Committee (IEC) at King Abdulaziz University Hospital
- 3. Saudi Food and Drug Authority (SFDA).

### **RISK AND BENEFITS**

There are possible risks associated with participating in this study include discomfort, headache, stomach awareness, nausea, vomiting, pallor, sweating, fatigue, drowsiness, disorientation, and apathy (Hicks & Durbin, 2011).; however, if the intervention is effective, people in the intervention group may experience reduced perioperative anxiety.

The participants will be monitored by the researcher continuously to assess for side effects. If a side effect occurs, the Virtual Reality session will be ceased immediately and treating doctor will be consulted.

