The Leiden Perioperative Patient Satisfaction questionnaire (LPPSq) is a valid and reliable tool used to assess and measure different aspects of patient satisfaction with perioperative care (Caljouw, Van Beuzekom, & Boer, 2008). This questionnaire consists of 39 questions which are divided over six dimensions; (1) information provision (four questions), (2) discomfort and needs (seven questions), (3) fear and concern (seven questions), (4) professional competence (four questions), (5) staff -patient relationship (14 questions), and (6) service quality (three questions). Patient satisfaction with

Study Protocol

perioperative care will be expressed by the mean satisfaction scores and the percentage of the maximum possible scores for each dimension (Caljouw et al., 2008). The participants will be asked to complete the questionnaire 24 hours after surgery before they are discharged (T4). This outcome will be collected by a research assistant at the research site, King Abdulaziz University Hospital.

4- Hospital Length of Stay (LOS) as measured from the date of admission to discharge from hospital.

The hospital length of stay is a proven recovery time indicator that can be used as a valid measure of robust outcomes in a variety of surgical fields and medical conditions (Laderman & Mate, 2016). The LOS will be measured in days that recorded on patients' discharge summary by subtracting the date of admission to hospital from the date of discharge from hospital (Abdelhak, Grostick, & Hanken, 2014). This outcome will be collected by a research assistant at the research site, King Abdulaziz University Hospital.

5- Adverse effect of VR intervention at any time point as measured by the Virtual Reality Symptom Questionnaire (VRSQ)

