The Virtual Reality Symptom Questionnaire (VRSQ) is a valid and reliable measure used to evaluate the possible occurrence of symptoms of cybersickness, a type of motion sickness caused by exposure to VR (Sevinc & Berkman, 2020). This questionnaire assesses eight general physical side effects, (1) general discomfort, (2) fatigue, (3) boredom, (4) drowsiness, (5) headache, (6) dizziness, (7) concentration difficulties, and (8) nausea. It also assesses five visual effects (1) tired eyes, (2) aching eyes, (3) eyestrain, (4) blurred vision, and (5) difficulties focusing on a seven-point range from 0 to 6, with 0 indicating that the symptom is not present and 6 that the symptom is severe. The potential participants in the intervention group will be asked to complete the questionnaire immediately before surgery (T2). This outcome will be collected by the PhD candidate.

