# Summary of Outcomes variables and Measures:

Variable	Scales/Questionnaires/instruments
Primary outcome	
Perioperative anxiety	Visual Analog Scale for Anxiety (VAS-A)
Secondary outcomes	
1. Stress level	Saliva cortisol test
	Mean Heart rate
2. Postoperative pain	Visual Analog Scale for pain (VAS-P)
3. Patient satisfaction	Leiden Perioperative Patient Satisfaction Questionnaire (LPPSQ)
4. Hospital Length of Stay (LOS)	Date of admission to the hospital from the date of discharge
5. Adverse effect of VR intervention	The Virtual Reality Symptom Questionnaire (VRSQ)

	S	TUDY P	PERIOD					
	Pre-admission	Preo	perative	ohase	Postoperative phase		Discharge	
TIMEPOINT**	-t 1	t o	t 1	t 2	t 3	t4	t 5	
ENROLMENT:								
Eligibility	х							
Informed consent	Х							
screen: using APAIS		Х						
Allocation		Х						
INTERVENTIONS:								
VR exposure				х				
ASSESSMENTS:								
Primary outcome:			x	Х	x			
Perioperative anxiety								
Secondary outcomes:			x	Х	x			
Stress level								
Postoperative pain			х		x			
Patient satisfaction						Х		
Length of hospital stay							X	
Virtual reality adverse effect				Х				

\*\*- $t_1$ : pre-admission; t0: on admission; t1: on admission to preoperative area; t2: immediately before surgery (holding area); t3: one-hour post-surgery; t4: after 24 hours post-surgery and before discharge; t5: discharge.

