# OTHER DATA

Participant's socio-demographic data and surgery data will be collected, including age, gender, marital status, education level, occupation, and type of surgery, type and dose of anaesthetic and previous surgeries. This data will be collected from the participant's health record by the PhD candidate.

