## BLINDING

The Research Assistant involved in outcome data collection will be blinded to the group allocation, as will the statistician who will conduct the analysis. Clinicians (nurses, doctors, and other healt h providers) will not be told who is participating in the study nor their group allocation; however, it is acknowledged that it is not possible to prevent participants from sharing this information with them.

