# STATISTICAL PLAN

Characteristics of groups will be summarised using counts and percentages for categorical variables and means and standard deviations for continuous variables. The primary outcome will be compared between groups at each follow-up time points using a linear mixed effects regression model, with fixed effects including treatment arm time (categorical), the interaction between treatment and time, and the baseline value of the outcome variable. Differences in mean VAS anxiety scores

between groups at each time point will be presented together with 95% confidence intervals and pvalue. Continuous secondary outcomes with repeated measurements will be compared using the same model. Hospital length of stay will be compared using the rank-sum test. Patient satisfaction and the VRSQ will be compared between groups using an independent sample t-test.

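### The between-group t-test planned for the VRSQ cannot be run, because only the VR arm completes it; the outcome's any-time-point wording also does not match its single measurement at T2

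*Protocol*

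**What the plan says.** Four parts of the protocol bear on this point.

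- **Definition** (Secondary Outcomes, outcome 5): "Adverse effect of VR intervention at any time point as measured by the Virtual Reality Symptom Questionnaire (VRSQ".
- **Who completes it, and when** (same section): "The potential participants in the intervention group will be asked to complete the questionnaire immediately before surgery (T2". The schedule in the summary of outcomes marks VR adverse effects at t2 only. Its footnote defines t2 and the later points as "immediately before surgery (holding area); t3: one-hour post-surgery; t4: after 24 hours post-surgery and before discharge; t5: discharge".
- **Analysis** (Statistical Plan): "Patient satisfaction and the VRSQ will be compared between groups using an independent sample t-test". No other analysis of the VRSQ is named.
- **Conduct of the session** (Risk and Benefits): "The participants will be monitored by the researcher continuously to assess for side effects", followed by "If a side effect occurs, the Virtual Reality session will be ceased immediately and treating doctor will be consulted".

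Under Intervention and Control, the control group receives standard care without VR.

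**The concern.** The analysis section assumes VRSQ scores from both arms; the outcome section collects them from one. Both cannot hold. The VRSQ is the only measure attached to the VR adverse-effect outcome, and the t-test is the only analysis attached to the VRSQ. A replacement would therefore have to be chosen later, possibly with the data in view.

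The definition has a related, smaller fault. It claims adverse effects at any time, while measurement happens once, before surgery. A reader of the trial report could take a low symptom count to cover recovery and discharge as well, when it covers only the interval from exposure to T2.

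**Working it through.** **1. The ceiling on the number of forms.** Inputs from the Sample Size section: difference 0.5 SD, power 80%, type 1 error 5% (two-sided assumed, since sidedness is not stated), dropout 15%.

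- n per arm = 2 × (z₀.₉₇₅ + z₀.₈₀)² / 0.5² = 2 × (1.960 + 0.842)² / 0.25 ≈ 62.8, rounded up to 63.
- Allowing for dropout: 63 / 0.85 = 74.1, rounded up to 75 per arm, so 150 in total.

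The stated sample size reproduces. It does not depend on the VRSQ; it matters here only because it fixes the largest possible number of forms.

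**2. Forms by arm.** One administration in the VR arm, none in the control arm:

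| | VR arm | Control arm |
|---|---|---|
| As randomised | 75 × 1 = 75 | 75 × 0 = 0 |
| With the 15% dropout allowance | 75 × 0.85 = 63.75, about 64 | 0 |

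The second row is illustrative. The protocol does not say when dropout occurs, and the form is completed before surgery on the day of exposure, so the loss could be smaller. The control column is 0 either way.

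**3. The planned test.** The two-sample statistic is t = (mean₁ − mean₀) / √[s² × (1/n₁ + 1/n₀)]. With n₀ = 0 there is no control mean and 1/n₀ is undefined. Running the test with 75 values against an empty group returned no statistic, degrees of freedom or p-value.

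**4. The rest of the same sentence.** The patient satisfaction questionnaire is asked of participants without restriction to one arm, so its between-group test can be run. Only the VRSQ half of the sentence fails.

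**5. Definition against measurement.** Outcome 5 claims any time point; the text and the schedule agree on T2 alone. Exposure lasts 5 to 10 minutes in the holding area, and T2 is the assessment after it and before surgery. The timing is sensible; the label is too wide.

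**The case against.** The strongest case for leaving the plan alone is that little depends on it. The primary analysis does not use the VRSQ, the natural substitute is a one-arm summary with no treatment effect to bias, and T2 is the right moment to ask. After surgery and anaesthesia, nausea, drowsiness or headache could not readily be attributed to VR. All of this stands, and it is why the point is minor. It does not remove the contradiction: a separate analysis plan could name a workable analysis only by overriding one of the two protocol statements.

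A reader might infer more than the protocol supports, in three ways.

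- **That stopped sessions will go unrecorded.** Stops are not among the outcomes, and the Other Data section lists "socio-demographic data and surgery data will be collected, including age, gender, marital status, education level, occupation, and type of surgery" and further surgical details. But that section concerns background data and its list is open-ended. Nothing in the protocol says stops will not be recorded, and a case report form or analysis plan not shown may cover them. Nor does the VRSQ instruction exempt patients whose session was stopped, so their symptoms can still be scored.
- **That measuring at one of the four points from t2 to t5 leaves three quarters of the follow-up uncovered.** This count treats the postoperative points as places where the VRSQ ought to have been given. For the reason above, they are not.
- **That the VRSQ is deficient because vomiting, pallor and sweating, named as risks, have no item of their own.** The VRSQ is a fixed 13-item instrument and the risk list is a general statement; they need not match. All three are observable signs within the scope of the continuous monitoring.

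**Conclusion.** Wrong as written, and minor. The between-group VRSQ comparison has up to 75 forms on one side and 0 on the other and cannot be computed. The outcome's any-time-point wording conflicts with a single administration at T2. The conclusion rests on taking the intervention-group-only instruction literally; if both arms were meant to complete the form, then that instruction is the sentence in error, and the two sections still disagree.

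The primary outcome, the sample size and the arrangements that protect participants are unaffected. How often sessions will be stopped cannot be estimated, because the protocol gives no stop rate, and no claim is made about it.

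**What to change.** 1. **Statistical Plan.** Remove the VRSQ from the t-test sentence and leave patient satisfaction there. Add that the VRSQ will be summarised in the VR arm only: for each of the 13 symptoms, the number and percentage scoring above 0, the median and the range.
2. **Secondary Outcomes, outcome 5.** Replace the any-time-point wording with: from VR exposure to T2. Keep the single administration at T2.

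These are two wording changes with no new data collection. Their limit is that a one-arm summary cannot separate symptoms caused by VR from fatigue, headache or drowsiness that patients awaiting surgery may have anyway. If that separation is wanted, the alternative is to give controls the VRSQ at T2 and keep the comparison, at a cost of up to 75 more forms of 13 items (75 × 13 = 975 answers) just before surgery.

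Optional, and not a correction of an error: report the number of VR sessions stopped early for a side effect alongside the VRSQ, recorded by the researcher who already monitors the session. This costs a few form fields.
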